6.2 Secondary objectives

6.2.1 Variables

Forced Expiratory Volume in 1 second (FEV1), 3 seconds (FEV3), 6 seconds (FEV6), FEV1% predicted, Forced Vital Capacity (FVC), FVC% predicted and Forced Expiratory Flow 25-75% (FEF25-75%) will be measured at screening, pre-dose, and specific time points for approximately 24 hours post dose (on Days 14 and 15) in each treatment period. Additional lung function parameters will be derived mathematically from the listed measurements (e.g. FEV1/FVC, FEV1/FEV6, FEV3/FVC, FEV3/FEV6, 1-FEV3/FVC, 1-FEV6/FVC).

For each patient, the spirometric measurements must be taken at approximately the same corresponding time of day in each treatment period as closely as practically possible.

Pre-bronchodilator FEV1, FEV3, FEV6, FVC, and FEF25-75 assessments will be conducted at screening.

Spirometry timepoints following the last dose of study medication in each treatment period are as follows:

- Day 14 predose: - 45 min and -15 min
- Day 14/15 post-dose: 5 min, 15 min, 30 min, 1 h, 2 h, 3h, 4 h, 8 h, 12 h, 23 h 15 min, 23 h 45 min

Time to peak FEV1 (maximum FEV1 post treatment) on Day 14 will be derived from the spirometry timepoints following the last dose of the study medication in each treatment period.

Standardized FEV1 AUC (0-4hr) (i.e. Area Under Curve between 5 min (=time 0h) and 4h post dose) on Day 14 of treatment. Area under curve for FEV1 from Spirometry data and will be calculated by trapezoidal rule as follows:

$$AUC_{0-T} = \frac{\sum_{i=1}^n (t_i - t_{i-1}) * (c_i + c_{i-1})}{2}, \text{ with } t_0 = 0 \text{ and } t_n = T$$

Where 't' is time-point and 'c' is FEV1 at time-point t.

T0 is initial time-point, Tn is the last time point of interest.

Peak FEV1 defined as the highest bronchodilatory effect on FEV1 during a period of 5 min to 4h on Day 14 of treatment. FEV1 measurements to consider defining peak FEV1 are on day 14 +5 min, +15 min, +30 min, +1h, +2 h, +3h, +4h.

PEF will be recorded twice daily using a Peak Flow Meter device, once in the morning and once approximately 12 h later in the evening. The morning/evening and overall (average of both morning and evening) PEF measurements will be averaged separately between days 8 to 14 of each treatment period and each subject.

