6.2.3.1 Model checking procedures

For the FEV1 AUC (0-4hr) if an observation is missing between two non-missing observations, the AUC will be linearly interpolated between the two non-missing values i.e. the subject's profile will be assumed to be linear between the two available values. Multiple occurrences of such missing values (an observation missing between adjacent non-missing observations) will be handled in a similar manner. But in case of missing consecutive assessments, then the patient profile will be excluded from analysis. No imputation will be made if either the first or the last observation is missing and AUC (0-4hr) is calculated from the available part of the profile ignoring the first and last time points.

For all secondary end points, if a patient takes rescue medication within 6h prior to the spirometry assessments and the visit is not rescheduled to the next day then all spirometry assessments data from this visit and the following visits in this treatment period will be set to missing. If rescue medication is taken during the 24 hour spirometry assessments then from the time of the rescue medication intake, all post-time point spirometry assessments will be considered as missing in this treatment period and AUC (0-4hr) will be considered as missing.

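### As written, SAP 6.2.3.1 voids FEV1 AUC(0-4h) after rescue use at any time in the 24-hour session, including rescue after the 4 h reading that cannot have affected it

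*SAP*

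**What the plan says.** The rule is in SAP 6.2.3.1, for all secondary spirometry endpoints. Its trigger is rescue use at any point in the 24-hour session. Once rescue has been taken, the SAP states: "all post-time point spirometry assessments will be considered as missing in this treatment period and AUC (0-4hr) will be considered as missing". The first consequence works forward from intake. The second, for AUC(0-4h), has no timing condition.

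SAP 6.2.1 defines the AUC as the "Area Under Curve between 5 min (=time 0h) and 4h post dose". Peak FEV1 uses the same seven readings: "FEV1 measurements to consider defining peak FEV1 are on day 14 +5 min, +15 min, +30 min, +1h, +2 h, +3h, +4h". The session continues with readings at 8 h, 12 h, 23 h 15 min and 23 h 45 min.

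SAP 6.2.3.1 also has general rules for missing AUC readings. A single gap is interpolated. For a missing end point the rule is: "No imputation will be made if either the first or the last observation is missing and AUC (0-4hr) is calculated from the available part". For longer gaps it is: "But in case of missing consecutive assessments, then the patient profile will be excluded from analysis".

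For the primary endpoint, SAP 6.1.3.1 removes readings only from the time of rescue onwards. The protocol's set-to-missing rule (11.1 and 11.4.3) concerns primary-endpoint data obtained after rescue. Neither has a clause that reaches back to earlier readings.

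**The concern.** Rescue taken after the 4 h reading cannot change a value measured at or before 4 h. Voiding the AUC in that case discards a complete, unaffected profile. It also makes the SAP inconsistent with itself: the 5 min to 4 h readings remain usable for peak FEV1 and the by-time model but not for the AUC computed from them.

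Standardized FEV1 AUC(0-4h) is a listed secondary measure (Protocol 2.2, SAP 1.3.2), analysed with the primary ANOVA. Precision is lost for no benefit. Rescue use is also an outcome that the trial compares with placebo, so the deletion may depend on treatment and on lung function in that period. If it does, low placebo values that were validly measured are removed selectively, and the indacaterol-placebo difference is pulled toward zero.

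**Working it through.** **1. What the clause does, by time of intake (logic only).**

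| Rescue taken | AUC readings removed by the forward rule | General missing-reading rules alone | Added effect of the AUC clause |
|---|---|---|---|
| In session, before the 3 h reading | at least 3 h and 4 h | profile excluded (consecutive gaps) | none |
| Between 3 h and 4 h | 4 h only | AUC from the available part | voids a truncated AUC: a real function |
| After the 4 h reading | none | AUC complete | deletes complete data |

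The last row covers (23.75 − 4)/23.75 = 83% of the post-dose session time.

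**2. Borrowed inputs.** The plan gives no SD or effect for AUC, so the illustration borrows those for trough FEV1 (Protocol 11.7): within-subject SD 230 mL, difference 170 mL. These reproduce the plan's sample size: 2 × (230 × (1.960 + 1.282)/170)² = 38.5, so 39, or 42 when rounded up to a multiple of six. With 20% dropout, 42/0.8 = 52.5, so 53, rounded to 54.

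**3. Which periods lose AUCs.** Each subject has one placebo and two active periods. With rescue rates p (placebo) and a (each active), placebo's share of lost AUCs is p/(p + 2a), which exceeds one half only if p > 2a.

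| p / a (assumed) | Placebo share |
|---|---|
| 5% / 5% | 33% |
| 10% / 5% | 50% |
| 28% / 13% | 28/54 = 52% |
| 17% / 6% | 17/29 = 59% |
| 20% / 5% | 67% |

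**4. Effect on the estimate.** This was simulated with 54 subjects, six sequences, a random-subject model, between-subject SD 700 mL (assumed), within-subject SD 230 mL and true difference 170 mL. The full-data SE is 230 × √(2/54) = 44.3 mL. The slope is the increase in log-odds of late rescue per SD lower FEV1 in that period. Every rescue rate and slope is an assumption. Monte Carlo error is about 2 mL.

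| Late rescue, placebo / active | Slope | Mean estimate | SE change |
|---|---|---|---|
| 17% / 6% | 0 | 170 mL (no bias) | +9% to +10% |
| 5% / 2% | 0.7 | about 165 mL | about +3% |
| 17% / 6% | 0.7 | about 153 mL | +10% |
| 17% / 6%, late rescue driven by a later FEV1 residual correlated 0.5 with the AUC residual | 0.7 | about 162 to 163 mL | +10% |
| about 28% / 13% | 1.0 | about 141 mL | about +20% |

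At 5%/2% the expected loss is 54 × 0.05 + 108 × 0.02 = 4.9 of 162 periods.

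A second setup used 42 completers and a within-subject ANOVA, and deleted every AUC with rescue at any time in the session. It gave the same direction: no bias at slope 0 (SE from 50 mL to 53-60 mL), and about 163 mL (10%/5%) to 145 mL (20%/5% and 30%/10%) at slope 0.7. At 30%/10% with a steeper slope of 1.2 it gave about 130 mL. The tabulated figures are therefore illustrations, not bounds.

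**The case against.** The best defence is that the authors meant only rescue that removes AUC readings. The clause has a real function between 3 h and 4 h, where it stops a truncated AUC from being used. That reading is reasonable, but the text does not contain it, and a programmer following the sentence would delete the later cases too. It makes this an unstated time limit to be written in, rather than evidence of a deliberate choice.

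A second defence is limited impact. One secondary endpoint is affected, the same readings still inform peak FEV1 and the by-time model, and any attenuation is conservative against placebo. All of this stands and limits the priority.

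A reader might infer two stronger claims. The first is that the data lost come mainly from placebo periods. The documents do not support that: it needs a placebo rate above twice the average active rate, and no session rates are given. The only directional statement on rescue use in the background data (Protocol 1.3.3.1) is for COPD. The most that can be said is that placebo periods lose AUCs at a higher rate if rescue is commoner on placebo.

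The second is that the rule does bias the result. Bias arises only if late rescue depends on that period's FEV1. If it does not, only precision is lost, and if the link to the early readings is weaker, the bias is smaller.

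**Conclusion.** The point holds as a defect in the wording of SAP 6.2.3.1. Followed literally, it discards complete AUC(0-4h) profiles because of rescue that came after the last reading used, and treats the same readings as valid elsewhere. The precision loss is certain whenever such rescue occurs. Attenuation is conditional on late rescue being commoner on placebo and in low-FEV1 periods.

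Its size cannot be fixed from the documents. The random-subject illustration runs from no bias to about 141 mL against a true 170 mL, with about 165 mL at the low rates, and rests wholly on assumed rescue rates and slopes and on trough FEV1 inputs. Trough FEV1 and the sample size are untouched. It is worth correcting because the correction is simple, not because a large distortion has been shown.

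**What to change.** Replace the final clause of the rescue sentence in SAP 6.2.3.1 with: *AUC(0-4h) will be considered as missing if the rescue medication was taken before the 4 h post-dose reading; rescue medication taken after the 4 h reading does not by itself make AUC(0-4h) missing.*

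Leave the rule for rescue within 6 h before the session, and the rules for missing observations, unchanged. This wording keeps the function between 3 h and 4 h and covers rescue taken in the session before the 5 min reading. It does not conflict with the exclusion for consecutive gaps. Nor does it depend on where the AUC starts, which SAP 6.2.1 puts at 5 min and SAP 6.2.3 at pre-dose. It would also help to report the number of AUCs set to missing, by treatment.

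The cost is one sentence and one programming condition, made before database lock. The existing forward rule already needs the time of intake, so no new data are required.

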6.2.3.2 Graphical presentation of results

Individual time profiles and Mean (SD) plots for all secondary parameters will be presented by treatment group and time.

The results of statistical analysis will also be presented in a graphical representation called forest plot showing the estimated mean differences indacaterol salts (acetate and maleate) to placebo and estimated difference between acetate and maleate salts and their confidence intervals per time point for each comparison including studentized residual plots.

6.3 Exploratory objectives

6.3.1 Variables

Not Applicable

6.3.2 Descriptive analyses

Not Applicable

7 Statistical methods for safety and tolerability data

7.1 Variables

Adverse events, vital signs (blood pressure, pulse rate, body temperature), ECG intervals, laboratory measurements, as well as subject demographics, baseline characteristics, and treatment information.

7.2 Descriptive analyses

Subject demographics and other baseline characteristics

All data for background and demographic variables will be listed by treatment sequence and subject. Summary statistics will be provided for all subjects, as well as for each treatment sequence.

Relevant medical history, current medical conditions, results of laboratory screens, drug tests and any other relevant information will be listed by treatment sequence and subject.

Subject disposition

A disposition summary will be presented for all subjects. This table will present the number and percentage of subjects who completed each study epoch and discontinued early for each epoch, along with the reasons for early discontinuation.

The number and percentage of subjects in each analysis set will be summarized for all subjects. All analysis set results will be presented in listings by treatment sequence and subject. A separate listing of all subjects excluded from any analysis set and the reasons for their exclusion will be provided.

All study epoch completion data will be listed by treatment sequence and subject.

Treatment

Data for study drug administration (rescue medication) and concomitant therapies will be listed by treatment sequence and subject.

Vital signs

All vital signs data will be listed by treatment sequence, subject, and visit/time and if ranges are available abnormalities (and relevant orthostatic changes) will be flagged. Summary statistics will be provided by treatment and visit/time.

ECG evaluations

All ECG data will be listed by treatment sequence, subject and visit/time, abnormalities will be flagged. Summary statistics will be provided by treatment and visit/time. Summary table for percentage and number of subjects with abnormal values <40 /40-90 />90 bpm in heart rate and summary table for percentage and number of subjects with notable values increase >30 / increase >60 / >450 />480/>500 msec in QTcF interval will be provided.

Clinical laboratory evaluations

All laboratory data will be listed by treatment sequence, subject, and visit/time and if normal ranges are available abnormalities will be flagged. A separate listing is provided presenting all parameters in a subject with any abnormal values. Summary statistics will be provided by treatment and visit/time.

Summary table for percentage and number of subjects with notable values for serum potassium (<3 /3-<3.5 />5.5 mmol/L) and plasma glucose (>10-15 />15 mmol/L) will be provided.

Adverse events

All information obtained on adverse events will be displayed by treatment and subject.

All treatment emergent adverse events will be summarized. Adverse events starting on or after the time of the first inhalation of study drug will be classified as a treatment emergent adverse event. Any adverse events that started during a washout period will be assigned to the treatment period just prior to that washout period. Any adverse events that started during the study before the time of the first inhalation of study drug of the first period will be classified as a prior adverse event and will not be summarized.

The number and percentage of subjects with treatment emergent adverse event will be summarized by treatment, overall by system organ class and preferred term, overall by system organ class, preferred term and maximum severity, suspected drug-related adverse events by system organ class and preferred term, serious adverse events by system organ class and preferred term, and adverse events leading to permanent discontinuation of study drug by system organ class and preferred term with a breakdown by treatment. A subject with multiple adverse events within a body system and treatment period is only counted once towards the total of this body system and treatment.

For the legal requirements of ClinicalTrials.gov and EudraCT, two required tables on treatment emergent adverse events which are not serious adverse events with an incidence greater than 5% and on treatment emergent serious adverse events and SAE suspected to be related to study treatment will be provided by system organ class and preferred term on the safety analysis set population.

If for a same patient, several consecutive AEs (irrespective of study treatment causality, seriousness and severity) occurred with the same SOC and PT:

- a single occurrence will be counted if there is ≤ 1 day gap between the end date of the preceding AE and the start date of the consecutive AE
- more than one occurrence will be counted if there is > 1 day gap between the end date of the preceding AE and the start date of the consecutive AE.

For occurrence, the presence of at least one SAE / SAE suspected to be related to study treatment / non SAE has to be checked in a block e.g., among AE's in a ≤ 1 day gap block, if at least one SAE is occurring, then one occurrence is calculated for that SAE.

The number of deaths resulting from SAEs suspected to be related to study treatment and SAEs irrespective of study treatment relationship will be provided by SOC and PT.

Protocol Deviations

Protocol deviations will be listed by treatment sequence and subject.

Liver events

Liver event data may be reported in listings and summaries if data is collected during the study.

7.3 Graphical presentation

Boxplots to visualize trends in longitudinal safety data (vitals, ECG, lab parameter) will be created.

Corporate Confidential Information
